6.4.6 Syncope

Medical history of syncope will be recorded at screening. At each study visit, the investigator should query the caregiver for occurrences of syncope since the last visit. An occurrence of syncope should be reported as an adverse event. If the caregiver reports an occurrence of syncope, the investigator should ask the "syncope adverse event questions" in Appendix G.

6.4.7 Somnolence

Medical history of somnolence will be recorded at screening. At each study visit, the investigator should query the caregiver for occurrences of somnolence from the last visit. An occurrence of somnolence should be reported as an adverse event. If the caregiver reports an occurrence of somnolence, the investigator should ask the "somnolence adverse event" questions in Appendix H.

6.5 Pharmacokinetic Assessments

At each predefined timepoint, PK samples will be obtained for measurement of concentrations of pimavanserin and its metabolite AC-279. When possible, an additional PK sample will be collected from subjects at any ET visit, or who experience a serious adverse event (SAE) or an adverse event (AE) leading to discontinuation, as soon as possible after the occurrence of that event.

For all PK samples (scheduled and unscheduled), the dates and times of administration of the last three doses of the study drug should be recorded. For samples collected from subjects who experience an SAE or an AE leading to discontinuation, the date and time of the last dose prior to the SAE or AE should also be recorded.

Pimavanserin and AC-279 plasma concentration data will remain blinded until the unblinding of the clinical database at the end of the study.

At the Baseline visit, a PK sample is drawn predose.

At Visit 3, Visit 5, Visit 8, or upon ET, a single PK sample will be collected at each visit within one of the following time intervals:

- 1-3 hours after dosing
- 4-7 hours after dosing
- 8-11 hours after dosing

Every effort should be made to collect a PK sample within each of the specified time intervals (1-3 hours after dosing, 4-7 hours after dosing, and 8-11 hours after dosing) over the course of the study visits that require a PK sample collection.

6.6 Blood Sampling

The involvement of experienced personnel in the conduction of blood drawing in this population is strongly recommended.

During blood sampling, measures to reduce pain are encouraged and can include application of numbing medication (e.g., lidocaine/prilocaine cream) to the draw site and/or use of a

Final Version: 1.0

Final Version: 1.0 Clinical Study Protocol Amendment 4 Date: 21 December 2022

winged infusion set (i.e., a "butterfly" needle). Mild sedation is allowed exceptionally for blood draws (e.g., alprazolam at a pediatric-appropriate dose per age, and the *lowest dose* deemed necessary by the Investigator) just in cases when the subject's agitation/anxiety does not allow a safe and accurate measurement and the Investigator, with agreement from the caregiver, considers it safe and appropriate for the subject.

A total of approximately four 2 mL venous blood samples will be collected from each subject for measurement of plasma pimavanserin and AC-279.

In addition, blood samples (one 2 mL sample) for determination of plasma concentrations of pimavanserin (and AC-279) will be collected in the event of ET, an SAE, or an AE leading to withdrawal.

Detailed procedures for collection, handling, and storage of plasma specimens are provided in the PK Laboratory Manual. Validated, sensitive, and specific high performance liquid chromatography-tandem mass spectroscopy (LC-MS/MS) assays will be used to measure pimavanserin and its metabolites in plasma.

An indwelling intravenous cannula may be used for collection of serial PK blood samples (saline is to be used to flush the indwelling cannula); otherwise, PK blood samples will be obtained via standard venipuncture procedures. The date and actual time of PK blood collection must be collected and recorded in the subject's eCRF. Each label will state the study number, subject number, analyte (plasma), study day, and scheduled sample time (plasma).

Each PK sample requires collection of 2 mL of venous blood. A single 2 mL venous blood sample will be collected for PK sampling from each subject at the Baseline visit. A single 2 mL venous blood sample will be collected from each subject on each subsequent day of PK sampling.

Table 6–2 tabulates the maximum allowable blood collection volumes by weight for affected children, and Table 6-3 and Table 6-4 summarize the blood volumes to be drawn from 6through 17-year-olds and 5-year-olds, respectively, in both a 24-hour and a 30-day period. The total amount of blood to be obtained from each subject should not exceed the allowable limits for affected children.

The total amount of blood to be obtained from each subject for PK analysis (approximately 8 mL) and safety laboratory blood samples (approximately 33 mL and 26.2 mL for 6- through 17-year-olds and 5-year-olds, respectively) during the course of this study will not exceed approximately 41 mL (6- through 17-year-olds) and 34.2 mL (5-year-olds). Note: this total amount does not account for additional blood samples that may be collected (e.g., to verify

eligibility, in the event of an SAE or an AE leading to withdrawal [see Section 7.4.2], to verify elevated laboratory results, etc.).

Table 6–2 Blood Collection Volume Limits in Affected Children

Weight	14 kg	15 kg	16 kg	17 kg
Maximum allowable blood volume in a 24-hour period	28 mL	30 mL	32 mL	34 mL
Maximum allowable blood volume in a 30-day period	56 mL	60 mL	64 mL	68 mL

Sources: North Shore LIJ Human Subject Protection Program Guidance Document, Maximum Blood Draw Limits, Version 11/24/14; National Center for Health Statistics (CDC) 2-20 years: Stature-for-age and weight-for-age percentiles

Notes: 5th percentile body weight for 5 year old girls≈14.6 kg; 5th percentile body weight for 5 year old boys≈15.1 kg

Table 6-3 Blood Collection Volumes for Safety Labs and Pharmacokinetic Samples (6- through 17-year-olds)

	Screening	Baseline	Visit 3	Visit 5	Visit 8
	Visit	Visit	(Week 1)	(Week 3)	(Week 6)
Total safety labs each study visit	9 mL	8 mL		8 mL	8 mL
PK - predose		2 mL			
PK - postdose			2 mL	2 mL	2 mL
Total PK samples each study visit		2 mL	2 mL	2 mL	2 mL
Total volume in any 24-hour period (Safety and PK)	9 mL	10 mL	2 mL	10 mL	10 mL
Total volume in any 30-day period (Sa	fety and PK)				
Screening and Baseline	19 r	nL			
Screening, Baseline, Week 1, and Week 3	31 mL				
Baseline, Week 1, and Week 3	22 mL				
Week 1 and Week 3			12	mL	
Week 3 and Week 6				20	mL

Abbreviation: PK=pharmacokinetics

Final Version: 1.0

Table 6–4 Blood Collection Volumes for Safety Labs and Pharmacokinetic Samples (5-year-olds)

	Screening Visit	Baseline Visit	Visit 3 (Week 1)	Visit 5 (Week 3)	Visit 8 (Week 6)
Total safety labs each study visit	8.5 mL	5.9 mL		5.9 mL	5.9 mL
PK - predose		2 mL			
PK - postdose			2 mL	2 mL	2 mL
Total PK samples each study visit		2 mL	2 mL	2 mL	2 mL
Total volume in any 24-hour period (Safety and PK)	8.5 mL	7.9 mL	2 mL	7.9 mL	7.9 mL
Total volume in any 30-day period (Sa	fety and PK)				
Screening and Baseline	16.4	mL			
Screening, Baseline, Week 1, and Week 3	26.3 mL				
Baseline, Week 1, and Week 3	17.8 mL				
Week 1 and Week 3	9.9 mL				
Week 3 and Week 6	15.8 n		8 mL		

Abbreviation: PK=pharmacokinetics

6.7 Safety Follow-up

A 30-day safety follow-up telephone contact is to be completed for subjects who complete the treatment period of the study and decide not to continue into the open-label study or are not eligible for the open-label study, as well as those who discontinue prematurely from the study. Subjects should have the following completed at 30(+3) days after last dose of study drug:

- Assessment of concomitant medications/treatments
- Assessment of AEs
- Assessment of syncope
- Assessment of somnolence

6.8 Unscheduled Visits

Unscheduled visits may occur as determined by the Investigator. The following safety assessments generally should be recorded at each unscheduled visit: assessment of AEs, assessment of syncope, assessment of somnolence, assessment of concomitant medications/treatments, measurement of vital signs and weight, the ESRS-A, and completion

Final Version: 1.0 Clinical Study Protocol Amendment 4 Date: 21 December 2022

of the C-SSRS. The Investigator may perform any additional safety evaluations deemed by the Investigator to be clinically indicated.

Every effort should be made to collect a PK sample at an unscheduled visit because of an SAE, or an AE leading to discontinuation.

6.9 **Remote Assessments or Visits**

Circumstances may arise (e.g., pandemic, natural disaster, political upheaval, or to minimize subject and caregiver burden) when on-site assessments of efficacy and/or safety may not be possible. In those cases, assessments may be performed offsite by raters either in person, or via video technology or telephone where possible. Remote visits are permitted for Week 2 (Visit 4) and Week 5 (Visit 7). For all other visits that are conducted remotely, the Investigator **must** contact the Medical Monitor for approval of the plan. Sites must keep a log to identify details of all visits that are administered remotely. For some remote efficacy assessments the vendor will provide additional training to ensure calibration to reduce discrepancy between on-site and remote assessments (ABC, CGI-S, RBS-R, VABS-Socialization). The location of the collected assessments should be captured in the eCRF.

Provided that the subject is physically in the clinic, and accompanied by a relative, all caregiver-rated assessments may be provided remotely.

7 ADVERSE EVENTS

7.1 **Specification of Safety Parameters**

7.1.1 **Definition of Adverse Event**

An AE is defined as "any untoward medical occurrence in a patient or clinical study participant, temporally associated with the use of study drug, whether or not considered related to study drug".

An AE can therefore be any unfavorable and unintended sign (e.g., an abnormal laboratory finding), symptom, or disease temporally associated with the use of a drug, without any judgment about causality or seriousness. An AE can arise from any use of the drug (e.g., off-label use, use in combination with another drug) and from any route of administration, formulation, or dose, including an overdose.

A suspected adverse reaction is any AE for which there is a reasonable possibility that the drug caused the AE.

AEs do not include the following:

Stable or intermittent chronic conditions (such as myopia requiring eyeglasses) that are present prior to Baseline and do not worsen during the study

 Medical or surgical procedures (e.g., surgery, endoscopy, tooth extraction, transfusion) or scheduled surgery/procedure. The condition that leads to the procedure is an AE if not present at time of consent.

- Overdose of concomitant medication without any signs or symptoms will not be considered an AE, but if a subject is hospitalized or has other serious criteria, the overdose will be considered an AE and shall be reported on the Sponsor's Overdose Reporting form.
- Hospitalization for elective surgery planned prior to study (situation where an untoward medical occurrence has not occurred)
- Pregnancy will not be considered an AE, but if it occurs, it will be reported on a pregnancy form

For subjects who enroll into the open-label extension study, AEs will be recorded from the time informed consent is obtained in the present study until the first dose of study drug in the open-label study.

For subjects who discontinue from the study or do not enroll into the open-label extension, AEs will be recorded from the time informed consent is obtained until 30 days after the last dose of study drug.

7.1.2 Definition of Serious Adverse Event

In addition to the severity rating, each AE will be classified by the Investigator as "serious" or "not serious." The seriousness of an event will be defined according to the applicable regulations and generally refers to the outcome of an event. An SAE is one that meets one or more of the following:

- Is fatal
- Is life threatening
- Results in disability or permanent damage
- Requires hospitalization (initial or prolonged)
- Results in congenital anomaly or birth defect
- Other serious event (medically significant/important medical event)

Definition of Life Threatening

A life threatening event places the subject at immediate risk of death from the event as it occurred. This does not include an AE, which, had it occurred in a more severe form, might have caused death.

Study: ACP-103-069 Clinical Study Protocol Amendment 4 Date: 21 December 2022

Definition of Hospitalization

Hospitalization is defined by the Sponsor as a full admission to the hospital for diagnosis and treatment. This includes prolongation of an existing inpatient hospitalization.

Examples of visits to a hospital facility that do **not** meet the serious criteria for hospitalization include:

- Emergency room visits (that do not result in a full hospital admission)
- Outpatient surgery
- Preplanned or elective procedures
- Protocol procedures
- Social hospitalization, defined as admission to the hospital as a result of inadequate family support or care at the subject's primary residence

Definition of Disability or Permanent Damage

Disability is defined as a persistent or significant incapacity or substantial disruption of the ability to conduct normal life functions.

Definition of Medically Significant

Important medical events (medically significant events) that may not result in death, be life threatening, or require hospitalization may be considered to be an SAE when, based upon appropriate medical judgment, they may jeopardize the subject or may require medical or surgical intervention to prevent one of the outcomes listed in this definition. Examples of such events are intensive treatment in an emergency room or at home for allergic bronchospasm, blood dyscrasias, convulsions that do not result in hospitalization, or development of drug dependency or drug abuse.

An SAE may also include any other event that the Investigator or Medical Monitor judges to be serious or that suggests a significant hazard, contraindication, side effect, or precaution.

7.2 Classification of an Adverse Event

7.2.1 **Severity of Event**

The severity of each AE will be assessed as described below and reported in detail as indicated on the eCRF:

- Mild: awareness of sign or symptom but easily tolerated, causing minimal discomfort, and not interfering with normal everyday activities
- Moderate: sufficiently discomforting to interfere with normal everyday activities

Final Version: 1.0

• Severe: incapacitating and/or preventing normal everyday activities

7.2.2 Relationship to Study Drug

The causality of each AE should be assessed and classified by the Investigator as "related" or "not related." An event is considered related if there is a reasonable possibility that the event may have been caused by the product under investigation (i.e., there are facts, evidence, or arguments to suggest possible causation).

Consider the following when assessing causality:

- Temporal associations between the agent and the event
- Response to drug cessation (de-challenge) or re-challenge
- Compatibility with known class effect
- Known effects of concomitant medications
- Pre-existing risk factors
- A plausible mechanism
- Concurrent illnesses
- Past medical history

7.2.3 Duration

The start and stop dates for AEs will be recorded using the following criteria:

- Start: Date of the first episode of the AE or date of worsening in severity
- **Stop:** Date when AE recovered or resolved, recovered or resolved with sequelae, or worsened in severity

7.2.4 Frequency

The frequency of the AE should be indicated according to the following definitions:

- Single: Experienced once, without recurrence at same severity
- **Recurrent:** More than one discrete episode with the same severity

7.2.5 Action Taken with Study Drug

- **Dose not changed:** No change in study drug
- **Drug interrupted:** Study drug temporarily stopped
- **Drug withdrawn:** Study drug discontinued permanently

Final Version: 1.0

- Not applicable
- Unknown

7.2.6 Therapy

None: No new treatment instituted

• **Medication:** New treatment initiated as a direct result of AE

• Other: Other action required

7.2.7 Outcome

Recovered/resolved: Recovered or resolved

• Recovered/resolved with sequelae: Recovered or resolved with sequelae

• Not recovered/not resolved: Not recovered or not resolved

• **Fatal:** Death due to an AE

• Unknown: Unknown

7.2.8 Seriousness

- Not serious
- Serious (see Section 7.1.2)

7.2.9 Definition of Unexpectedness

An AE, the nature or severity of which is not consistent with the information provided in the Reference Safety Information section of the current pimavanserin Investigator's Brochure.

7.3 Time Period and Frequency for Event Assessment and Follow-up

Adverse events will be recorded from the time informed consent is obtained through the study safety follow-up period. If an AE is ongoing at the end of the study safety follow-up period, every reasonable attempt should be made to follow and appropriately treat the subject until the AE resolves or until the Investigator deems the AE to be chronic or stable. If the subject rolls over into the open-label study, any ongoing AEs will be followed in the open-label study.

In the event that a subject discontinues from the study and has an ongoing AE at the time of discontinuation (Section 4.5.1), the subject should be followed and appropriately treated until the AE resolves or until the Investigator deems the AE to be chronic or stable. If a subject withdraws from the study because of an AE, no additional assessments may be performed (Section 4.4).

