For female subjects of childbearing potential, a serum pregnancy test will be completed at the Screening visit; urine pregnancy dipstick tests will be completed at all other scheduled timepoints.

- A urine toxicology dipstick should be used in addition to the urine toxicology screen at both the Baseline visit and Visit 8 (to confirm eligibility in Study ACP-103-070). A rapid UDS dipstick will be used at Visit 3.
- Study drug may be dispensed to the subject at unscheduled visits if needed.
- If visit is remote, accountability will be assessed verbally with the caregiver, and verified at the next clinic visit.
- The involvement of experienced personnel in the conduction of routine procedures such as blood drawing and ECG recording in this population is strongly recommended.
- The ET visit will not be done if the subject withdraws consent to participate in all parts of the study and withdrawal of consent happens before that timepoint.
- Prolactin results should be blinded to the Investigator and the Sponsor after Baseline. Results will be monitored by an independent Medical Monitor from the Contract Research Organization (CRO).
- Including COVID-19 vaccination.
- For scales that require caregiver input, the caregiver should be the parent/LAR or designee. A designee should be a family member, adult and responsible, living with or in very frequent contact with the subject participating in the study, that is committed to providing responses for the caregiver-reported scales for the duration of Studies ACP-103-069 and ACP-103-070. Caregivers providing input for the ABC, RBS-R, and CGSO scales will be trained in accurate symptom reporting (ASR) prior to completing the scales. The ASR training should be done at Screening before the caregiver completes any scales, and repeated whenever there is a change in caregiver or if the site feels a caregiver requires retraining.
- If visit is conducted remotely, vital signs, height, weight, and BMI are optional.
- As measured by stadiometer.
- The ESRS-A will only be conducted at clinic visits and not at remote visits.
- If the caregiver reports an occurrence of syncope, the investigator should ask the "syncope adverse event questions", as a tool to guide diagnosis, in Appendix G.
- If the caregiver reports an occurrence of somnolence, the investigator should ask the "somnolence adverse event questions", as a tool to guide diagnosis, in Appendix H.

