4.4 Subject Withdrawal of Consent

In accordance with the Declaration of Helsinki and other applicable regulations, a subject has the right to withdraw from the study at any time, and for any reason, without prejudice to his or her future medical care. If the subject (and/or parent/LAR) decides to withdraw consent from all components in the study, this must be documented and no additional assessments will be performed. The Sponsor may retain and continue to use any data collected before such a withdrawal of consent. The subject may request destruction of any samples taken and not tested, prior to their withdrawal of consent, and the Investigator must document this in the site study records.

If the subject (and/or parent/LAR) wants to discontinue treatment and agrees to the evaluations specified at the EOT/ET visit and/or at safety follow up (whichever is applicable), as outlined in Table S-1, the agreed assessments should be conducted. The

Final Version: 1.0

subject's reason for wanting to discontinue treatment and the agreement to continue with the applicable assessments for study termination must be documented.

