4.5.1 Handling of Subject Discontinuation During the Treatment Period

Unless the subject (or parent/LAR) has withdrawn consent from all components of the study, every reasonable effort should be made to complete Visit 8/ET and the safety follow-up visit (as outlined in Table S-1) if a subject discontinues prematurely during the treatment period of the study. All information will be reported on the applicable pages of the electronic case report form (eCRF). Every effort should be made to collect a PK sample at any ET visit, or the visit immediately following any SAE, or following any AE leading to discontinuation, even if it is an unscheduled visit.

If a subject is discontinued from the study treatment because of an AE, every reasonable attempt should be made to follow and appropriately treat (or refer for treatment) the subject until the AE resolves or until the Investigator deems the AE to be chronic or stable. For subjects who continue to be followed for safety, SAEs should continue to be reported as described in Section 7.4.2. All SAEs will continue to be followed and appropriately treated until such events have resolved or the Investigator deems them to be chronic or stable.

Final Version: 1.0

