4.8.2.1 Permitted, Restricted, and Prohibited Medications

Prohibitions and restrictions for concomitant medications should be followed between the initial screening visit and Visit 8 (EOT)/ET as specified in Appendix A and Appendix B. These appendices do not constitute an exhaustive list and any questions regarding prohibited and restricted medications should be discussed with the Medical Monitor or designee. The Investigator may prescribe appropriate medication to treat AEs.

Medications that can prolong QT interval are prohibited (or restricted) as specified in Appendix A.

Permitted concomitant medications should remain at a stable dose throughout the treatment period.

If a subject is on a medication restricted by the protocol, the medication should be adjusted if it is determined by the Investigator to be clinically appropriate (e.g., if the subject's symptoms are not well-controlled or if the subject cannot tolerate the current medication) in consultation with the treating physician.

Subjects who require current treatment with a prohibited medication will be withdrawn from the study.

Subjects who have taken a prohibited medication during the study will be withdrawn from the study unless:

- the prohibited medication has been discontinued, AND
- withdrawal from the study presents an unacceptable medical risk to the subject

The justification to allow the subject who has taken a prohibited medication to continue in the trial will be made by the Sponsor/Medical Monitor with medical input from the Investigator, and will be documented. If a subject is allowed to remain in the trial, this will be reported as a major protocol deviation and not a waiver.

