5.1.5 Blinding

Treatment assignments will be blinded to all study subjects, parents/LARs, Investigators, raters, site personnel, and Sponsor personnel. In the event of a potential suspected unexpected serious adverse reaction (SUSAR), in accordance with current health authority guidance, treatment assignments for the affected subject may be unblinded to a controlled group of the Sponsor's Safety and/or Regulatory personnel for reporting purposes.

If pregnancy occurs during the study, the pregnant subject should be withdrawn and unblinded so that counseling may be offered based on whether the fetus was exposed to the active drug or placebo.

Details regarding medical emergency unblinding procedures are provided in Section 9.9.

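### Protocol 7.3 ends assessments for anyone who withdraws because of an AE, whereas Sections 4.4 and 4.5.1 and Table S-1 tie this to withdrawal of consent from the whole study

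*Protocol*

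**What the plan says.** Protocol 7.3 closes with two consecutive rules. The first concerns discontinuation: if "a subject discontinues from the study and has an ongoing AE at the time of discontinuation (Section 4.5.1), the subject should be followed" and treated until the event settles. The second concerns withdrawal: "If a subject withdraws from the study because of an AE, no additional assessments may be performed (Section 4.4").

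The other sections use a different trigger:

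- **Section 4.4** applies when the subject or parent/LAR "decides to withdraw consent from all components in the study, this must be documented and no additional assessments will be performed". It then treats separately a subject who stops treatment but agrees to the end-of-treatment or follow-up evaluations: "as outlined in Table S-1, the agreed assessments should be conducted".
- **Section 4.5.1** says that after premature discontinuation "every reasonable effort should be made to complete Visit 8/ET and the safety follow-up visit". Its one exception is consent withdrawn from all components. It also asks for follow-up of subjects taken off treatment because of an AE, and for a PK sample.
- **Table S-1, ET note**: "The ET visit will not be done if the subject withdraws consent to participate in all parts of the study", provided that happens before the visit.
- **Section 3.1.3** exempts three groups from the 30-day call: roll-overs to the extension, full consent withdrawals and documented losses to follow-up. Subjects who leave because of an AE are not among them.
- **Section 6.6** lists an AE that leads to withdrawal as a reason to take a PK sample.

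**The concern.** Section 7.3 is where a site would look when a child leaves because of an AE. Read literally, its last sentence tells the site to do nothing more, even when the family would accept an ET visit. The section it cites does not say this.

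Safety data are what is at stake. Protocol 1.5.1 states that pimavanserin prolongs the QT interval, that dose-related QTc prolongation was seen in adolescents taking it with other psychotropics, and that it has not been studied as monotherapy in children and adolescents. Subjects who stop because of an AE are the ones in whom a final ECG and laboratory set is most informative. A site following 7.3 could skip the ET visit (ECG, laboratory tests, PK sample, ABC-I) and the 30-day call.

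**Working it through.** The conflict is textual, and the plan has no figure to reproduce. The check has three parts.

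**1. Compare the rules for one subject.** Take a subject who leaves because of an AE without withdrawing consent from all components.

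| Source | What decides | Result for this subject |
|---|---|---|
| 7.3, last sentence | Withdrew because of an AE | No further assessments |
| 7.3, preceding sentence | Discontinued with an ongoing AE | Follow the AE |
| 4.4 | Scope of consent withdrawn | Do the agreed assessments |
| 4.5.1 | Scope of consent withdrawn | Attempt ET visit, follow-up and PK sample |
| Table S-1, ET note | Scope of consent withdrawn | ET visit not waived |
| 3.1.3 | Listed exemptions | 30-day call is due |
| 6.6 | AE leading to withdrawal | Take a PK sample |

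Only the last sentence of 7.3 stops assessments.

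**2. Does the protocol's terminology rescue the sentence?** It would if *withdraw* always meant withdrawal of consent, but it does not. Under 4.8.2.1, "Subjects who require current treatment with a prohibited medication will be withdrawn from the study". Under 5.1.5, "the pregnant subject should be withdrawn and unblinded so that counseling may be offered". Section 6.4.4 withdraws a subject for an exclusionary ECG. Section 6.3.1 cites 4.4 for a discontinuation that the Investigator decides. The site is left to judge where discontinuing ends and withdrawing begins.

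**3. What is lost if a site follows 7.3.** The inputs are:

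- Post-baseline ECGs and safety laboratory tests are scheduled at Week 3 and Week 6/ET only (Protocol Table S-1 and 6.4.4; SAP 14.2 and 14.4).
- The ABC is done weekly.
- The Full Analysis Set needs one or more post-baseline ABC-I scores (Protocol 9.4; SAP 4).
- The planning allowance for discontinuation is up to 15% of 228 subjects, 76 per arm (Protocol 9.3).

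Assuming the ET visit is skipped and no unscheduled tests are added:

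| Time of leaving | Data | With ET visit | Without ET visit |
|---|---|---|---|
| Before Week 3 | ECG and laboratory sets | 0 + 1 = 1 | 0 |
| Between Week 3 and Week 6 | ECG and laboratory sets | 1 + 1 = 2 | 1 |
| Before the Week 1 visit | ABC-I scores | 0 + 1 = 1 | 0 (outside the Full Analysis Set) |

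An unscheduled visit would not by default fill the gap. The Section 6.8 list contains neither ECG nor laboratory tests, although the Investigator may add them. PK loss is less likely, because 6.8 asks for a sample at an unscheduled visit for an SAE or an AE leading to discontinuation.

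The SAP's overall post-baseline summaries of potentially clinically important values (14.2.1.3 and 14.4) use as denominator the subjects who have a post-baseline value. A subject with none leaves the denominator as well as the numerator.

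For scale, 0.15 × 228 = 34.2 leavers for any reason, and 0.15 × 76 = 11.4 per arm. Those who leave because of an AE and keep some consent are an unknown part of these.

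**The case against.** The strongest reply is that the text largely explains itself. Section 7.3 pairs discontinuing with 4.5.1 and withdrawing with 4.4. Section 4.4 is about consent and opens with the subject's own right to withdraw. The counter-examples from 4.8.2.1, 5.1.5 and 6.4.4 are passive, describing something done to the subject, and none of them cites 4.4 or stops assessments. The one in 6.4.4 is a Baseline eligibility matter. The 6.3.1 citation can be read as pointing to the paragraph of 4.4 on stopping treatment with agreed assessments. The correct rule also appears in 3.1.3, 6.5, 6.7, 7.1.1 and 7.4.2, and SAP 13.1.1 expects ET evaluations to be completed. For data to be lost, a site must override all of these, the family must still consent, and no Investigator may add an ECG or laboratory tests.

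Much of this stands. The intended meaning was probably full withdrawal of consent, and the chain to actual data loss is conditional at each step. Strictly, 4.4 and the Table S-1 note say when assessments stop, not that they stop in no other case; 4.5.1 is the section that makes full consent withdrawal the exception.

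The reply does not remove the conflict. Section 4.4 itself separates full withdrawal from stopping treatment with agreed assessments. Even read as a sentence about consent, 7.3 drops the qualifier that decides which of the two applies.

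**Conclusion.** The inconsistency is real, and the last sentence of 7.3 is wrong as written. It should be corrected. The defect is minor to moderate, because the right rule stands elsewhere and harm requires a literal reading by a site.

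Under that reading, and with no unscheduled tests, each affected subject loses one post-baseline ECG and laboratory set. For a leaver before Week 3 it is the only one, and that subject also leaves the overall denominators for potentially clinically important values. The documents give no rate of AE withdrawal with retained consent, so the number of such subjects is unknown.

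The efficacy effect is small: only a leaver with no ABC-I score before the ET visit would fall out of the Full Analysis Set. Nothing here changes the estimand, the primary test or the power.

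**What to change.** Replace the last sentence of Protocol 7.3 with:

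> If a subject (or parent/LAR) withdraws consent from all components of the study, including because of an AE, no additional assessments will be performed (Section 4.4); otherwise the ET visit, PK sample, safety follow-up and AE follow-up in Section 4.5.1 apply.

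This restates the rule already in 4.4 and 4.5.1. The cost is one sentence in the protocol, with no new visits or procedures and no change to the SAP.
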